TITLE: Use of tolvaptan, a vasopressin antagonist, to increase urine dilution and reduce cystine urolithiasis among patients with homozygous cystinuria: a pilot investigation

NCT02538016

Latest IRB Approval Date: 9/23/2019

A. Specific Aims/Objectives

The goal of this research project is to establish that in short-term use, tolvaptan is a safe and potentially effective new therapy for cystinuria, by conducting a short-term pilot study of the safety and tolerability of this drug, and assess impact on urinary stone risk parameters, among adolescent and young adult patients with clinical cystinuria.

Specific Aim 1) To characterize the short-term safety profile of tolvaptan therapy in adolescent patients with cystinuria.

Hypothesis 1a: Tolvaptan will be well tolerated with low adverse effects, minimal disruption of serum electrolytes, and no detectable alterations in blood pressure and other cardiovascular parameters

Specific Aim 2) To characterize the short-term effect of tolvaptan on urinary risk factors for urolithiasis in adolescent patients with cystinuria.

Hypothesis 2a: Tolvaptan therapy will result in >25% increased urine output, decrease in urinary osmolality of >25%, and increase in urinary cystine capacity of >25%

B. Background and Significance

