All information will be collected and reported onto a paper case report forms (CRFs), which will later be entered into REDCap. 24 hour urines and clinical (vital signs, weights, fluid intake and output, thirst and dry mouth) and laboratory data (urine cultures/analysis, serum electrolytes and liver function tests) will be collected throughout the duration of the patient's participation in the research study. The following table indicates the procedures that will be done each day the patient is involved with the research study:

3-6 days before	Day 0	Day 1	Day 2	Day 3
-----------------	-------	-------	-------	-------

Day 0				
24 hour urine collection.	CTSU-Outpt. Physical exam. Blood sample. Urine sample.	CTSU – admitted. Tolvaptan given orally. Urine sample.	CTSU – discharged Tolvaptan given orally. Blood sample. Urine Sample	CTSU – outpatient. Tolvaptan given orally. 24 hour urine collection.

Day 4	Day 5	Day 6	Day 7	Day 8
CTSU – outpatient. Tolvaptan given orally. Blood sample.	CTSU – admitted. Tolvaptan given orally. Urine sample.	CTSU – discharged. Tolvaptan given orally. Blood sample. Urine Sample	CTSU – outpatient. Tolvaptan given orally. 24 hour urine collection.	CTSU – outpatient. Tolvaptan given orally. Blood sample.

Day 9	Day 10	3-6 days after Day 10
CTSU – outpatient. No medication given. .Urine sample	CTSU – outpatient. No medication given. Blood sample.	24 hour urine collection.

(6) Study Timeline (as applicable)

The study will be conducted through the Clinical and Translational Study Unit at Boston Children’s Hospital. The treatment period will for 8 days. Subjects will be spend two 24-hour periods under inpatient observation; the remainder of the period will be under outpatient observation, with daily visits to the CTSU. The day prior to the treatment period (Day 0) will be used to obtain baseline clinical and laboratory data. Study drug will be administered starting on Day 1 through Day 8, with a 2 day washout period on days 9 and 10. Patients will be monitored during the period with 24-hour urine collection for cystine stone risk profile, daily weights, vital signs, blood draws, fluid intake and output, and assessment of subjective outcomes.

E. Adverse Event Criteria and Reporting Procedures

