Subjects will be monitored for drug tolerability and safety. Patients will be observed in the inpatient CTSU setting for 24 hours after the initial dose (Day 1) and also for 24 hours after the increased dose (Day 5). During each of these 24 hour periods, subjects will undergo around the clock monitoring of vital signs and daily input and outputs.. On Day 2-4 and Day 6-8 subjects will be monitored on an outpatient basis, coming in each day to the CTSU. At each outpatient visit vital signs will be checked. Serum Electrolytes will be checked on days 0, 2, 4, 6, 8,and 10. Liver function tests will be obtained at baseline, Day 4, and Day 8, and Day 10. Thirst and dry mouth will be assessed daily with visual analog scales. (31-33).

Criteria for cessation of treatment will include abnormal serum sodium (>5 mmol/L above or below normal range), potassium (>0.2 mmol/L above or below normal range), or CO₂ (>2 mmol/L above or below normal range). Other criteria will include unstable vital signs (e.g. tachycardia, hypotension), intolerable subjective symptoms of thirst or voiding symptoms, or other symptoms subjectively attributed to the medication.

Subjects that experience adverse reaction at the higher dose level will be reduced to the lower dose level; if adverse effects persist at the lower dose level, the study drug will be discontinued.

For other potential adverse events not listed above, the investigators will decide on a case-by-case basis whether treatment should be continued, taking the subject's short-term and long-term health and safety as the primary factor for consideration.

F. Data Management Methods

Clinical and laboratory data will be maintained in a secure REDCap database.

G. Quality Control Method

Trained research personnel will be collecting data and entering it into REDCap. There also will be data checks within the REDCap system.

H. Data Analysis Plan

In this pilot study, the primary analysis will be description of the change from baseline during treatment of cystine stone risk profile. This will be demonstrated graphically. With respect to the primary endpoint, differences in cystine capacity between baseline and low-dose treatment phase, and between baseline and the high-dose treatment phases, will be compared with paired t-tests. Data regarding thirst and dry mouth will also be recorded and demonstrated graphically.

I. Statistical Power and Sample Considerations

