As a pilot study with very low numbers of subjects, statistical analysis will not be feasible for adverse effects. Adverse effects will be classified with respect to whether they resulted in the subject discontinuing study medication or requiring additional monitoring, testing, or treatment, or not. For electrolyte and cardiovascular measures, we will analyze these outcomes according to proportion of subjects experiencing at least one outlier measurement (defined as a clinically abnormal value based on the standard normal range for each test) for each parameter (each of the serum chemistry values, and cardiovascular measures).

J. Study Organization

Data for this study will be managed via the REDCap web-based data management system at Boston Children's Hospital. This database will store patient-level variables and clinical outcome data. PHI on individual study participants will be maintained in a password protected database. Data within the PHI database will be linked to the clinical data in the primary database via study identification numbers.

K. References

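### Electrolytes and cardiovascular measures are summarised only by whether a subject ever has an abnormal value; no change from Day 0 is planned, so Hypothesis 1a's prediction of no alteration has no matching analysis

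*Combined protocol and SAP*

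**What the plan says.** Hypothesis 1a (Section A) predicts, among other things, "minimal disruption of serum electrolytes, and no detectable alterations in blood pressure and other cardiovascular parameters".

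Section I gives the only analysis named for these measures: for each serum chemistry value and cardiovascular measure, the "proportion of subjects experiencing at least one outlier measurement (defined as a clinically abnormal value based on the standard normal range for each test". It does not say which days count. Its remark that statistical analysis is not feasible is confined to adverse effects.

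The data for a change analysis are largely there. Section D(6) states: "The day prior to the treatment period (Day 0) will be used to obtain baseline clinical and laboratory data". The Day 0 entry in the Section D(5) table reads "CTSU-Outpt. Physical exam. Blood sample. Urine sample". Section E states: "Serum Electrolytes will be checked on days 0, 2, 4, 6, 8,and 10". On vital signs it states: "At each outpatient visit vital signs will be checked". It adds round-the-clock monitoring in the inpatient periods, "24 hours after the initial dose (Day 1) and also for 24 hours after the increased dose (Day 5").

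Change from baseline appears only in Section H. There it refers to the cystine stone risk profile, which Section D(6) ties to 24-hour urine, with paired t-tests for cystine capacity.

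**The concern.** Whether a measure is altered is a question about change within a subject. A subject can move from Day 0 and stay in range, or be out of range on Day 0 and not move at all. The planned proportion does not separate these cases, and it counts a rise and a fall alike.

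The mismatch is clearest for blood pressure and the other cardiovascular parameters, where the hypothesis is that no alteration can be detected. It is less clear for electrolytes, because minimal disruption can fairly be read as few abnormal values.

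A small directional shift is plausible on the protocol's own account: Section C reports a minor rise in plasma osmolality in both adult cystinuria patients previously given the drug. What is at stake is that a low proportion of flagged subjects could be reported as support for Hypothesis 1a although no change had been estimated.

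**Working it through.** **Inputs from the documents.** Section D(2): 8 complete participants out of 16 recruited. Section E: electrolytes on Days 0, 2, 4, 6, 8 and 10, which is one baseline, four on-treatment and one washout draw. The plan gives no figure of its own to reproduce on this point: no SD, correlation or effect size for these measures.

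**Assumptions not in the documents.** The normal range covers 95% of values (limits at ±1.96 SD, where SD is that of a single reading). Every out-of-range value counts as clinically abnormal. Readings are normal with equal within-subject correlation ρ. The drug shifts Days 2 to 8 by the same amount in every subject. The range is 3.92 SD wide, so 0.5 SD is about 1/8 of the width and 1 SD about 1/4.

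**Step 1: planned proportion, any of six draws abnormal.** At ρ = 0 it can be done by hand.
- No shift: 1 − 0.95^6 = 0.265.
- 0.5 SD: an on-treatment draw stays in range with probability Φ(1.46) − Φ(−2.46) = 0.921, so 1 − 0.921^4 × 0.95^2 = 0.351.
- 1 SD: Φ(0.96) − Φ(−2.96) = 0.830, so 1 − 0.830^4 × 0.95^2 = 0.572.

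Other correlations are by simulation. Extra subjects = 8 × (shifted rate − no-shift rate).

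| | ρ = 0 | 0.5 | 0.7 | 0.9 |
|---|---|---|---|---|
| No shift | 0.265 | 0.207 | 0.164 | 0.109 |
| 0.5 SD | 0.351 | 0.271 | 0.221 | 0.159 |
| 1 SD | 0.572 | 0.442 | 0.376 | 0.293 |
| Extra of 8, 0.5 SD | 0.7 | 0.5 | 0.5 | 0.4 |
| Extra of 8, 1 SD | 2.5 | 1.9 | 1.7 | 1.5 |

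If the word clinically implies a stricter threshold (a 99% range), the no-shift rates fall to 6%, 5%, 4% and 3%, and the 1-SD rates to 23%, 17%, 15% and 11%.

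**Step 2: paired change.** Take the mean of the two draws in a dose phase minus Day 0. Its variance is (1 + ρ)/2 + 1 − 2ρ = 1.5(1 − ρ), so the SD is 1.225, 0.866, 0.671 and 0.387. The 95% CI half-width is 2.365 × SD/√8. The chance that the CI excludes zero comes from the noncentral t with 7 degrees of freedom.

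| | ρ = 0 | 0.5 | 0.7 | 0.9 |
|---|---|---|---|---|
| Half-width (SD) | 1.02 | 0.72 | 0.56 | 0.32 |
| CI excludes zero, 0.5 SD | 0.17 | 0.29 | 0.44 | 0.88 |
| CI excludes zero, 1 SD | 0.51 | 0.80 | 0.95 | >0.99 |

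**Step 3: the count as a detector of a 1-SD shift.** Take the no-shift rate as known, find the smallest count k of 8 with P(X ≥ k) ≤ 0.05, and compute the chance of reaching k.
- All six draws: k = 5, 5, 4, 3; chance 0.53, 0.25, 0.35, 0.43.
- Days 2 to 8 only: no-shift rates 0.186, 0.156, 0.130, 0.094; 1-SD rates 0.525, 0.396, 0.337, 0.261; k = 4, 4, 4, 3; chance 0.69, 0.40, 0.27, 0.35.

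At ρ = 0 the count does as well as paired change (six draws) or better (Days 2 to 8). From ρ = 0.5 upward paired change is ahead on either window. The count is somewhat handicapped because it is discrete: with six draws its attained level is 0.012 to 0.047 rather than 0.05.

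**Step 4: does this carry over to vital signs?** No. The number of readings is not stated. With 20 readings, an arbitrary figure, all shifted by 0.5 SD, the extra flagged subjects number 1.3 at ρ = 0 (no-shift rate 64%) and 0.4 to 0.7 at ρ = 0.5 to 0.9.

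**The case against.** This is an uncontrolled pilot with 8 completers, and counting abnormal values is a standard safety summary. It also matches Section E, whose cessation criteria are set against the normal range, for example "abnormal serum sodium (>5 mmol/L above or below normal range"). Marked disturbances may appear a second time, through Section I's classification of adverse effects by whether they led to discontinuation or to further monitoring, testing or treatment. A large shift would show in the proportion itself. The documents give no within-subject correlation, and at correlation 0 paired change has no advantage for a 1-SD shift.

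All of that stands, and it keeps the point minor. It does not remove it: neither the proportion nor the adverse-effect classification gives the size or direction of a shift within range. The small sample is no reason to omit an estimate, since Section H already plans paired t-tests on cystine capacity at this size.

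Two stronger readings are tempting. A reader might infer that Aim 1 goes unassessed or that the planned proportion is invalid; the documents support neither. A reader might also take the electrolyte figures as showing how insensitive the plan is for blood pressure; without a stated number of readings they do not.

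**Conclusion.** The point holds as a mismatch between Hypothesis 1a and its analysis. It is firm for the prediction that blood pressure and other cardiovascular parameters are not detectably altered, and weaker for electrolytes. This rests on the text alone: no section plans change from Day 0 for these measures.

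The numerical illustration applies to electrolytes only and depends on the assumed 95% ranges and correlations. Under them the proportion responds weakly to a modest shift and moderately to a 1-SD shift. Paired change is the more sensitive summary if repeat values within a subject correlate at about 0.5 or more. At any correlation it adds a direction and an interval, although a wide one.

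The priority is minor. No primary endpoint, data collection or stopping rule is affected.

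**What to change.** In Section I:

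1. Keep the outlier proportion. Count values after the first dose through Day 8, and show Day 0 and washout abnormalities separately. State whether clinically abnormal means any out-of-range value or requires judgement.
2. For each serum chemistry value, blood pressure and heart rate, add individual trajectories and mean paired change from Day 0 with a 95% CI by dose phase. For electrolytes the phases are Days 2 and 4, and Days 6 and 8. Label by the dose actually taken, since Section E allows a reduction.
3. For vital signs, compare outpatient readings with the outpatient Day 0 reading and show inpatient readings separately, because the setting differs. Days 2 and 6 are discharge days, so state where their readings belong. Confirm that vital signs are taken on Day 0; they are implied by the baseline visit but not named.
4. Include every dosed subject with a Day 0 value and at least one post-dose value, and use values up to stopping. List early stoppers with their last values, so that subjects stopped for abnormal results are not lost from the summary.
5. Label the estimates descriptive, unadjusted for multiplicity and not a test of absence of effect.

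The cost is about a paragraph of text and more tables; the electrolyte draws are already scheduled. Intervals will be wide with 8 subjects, and about 5% will exclude zero by chance. With six parameters (sodium, potassium, CO2, systolic and diastolic pressure, heart rate) in two phases, that is 12 × 0.05 = 0.6 intervals. If the three vital signs also carry separate inpatient intervals, it is 18 × 0.05 = 0.9, and further analytes add more.

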Non-cutaneous malignancy within last 5 years

History of adverse reaction or allergy to Tolvaptan or other arginine vasopressin V₂-receptor antagonists

Positive pregnancy test

Currently breastfeeding

Inability or unwillingness to consent/assent

(3) Description of Study Treatments or Exposures/Predictors

Starting at between 10AM and 2PM on Day 1, Tolvaptan will be administered orally. See dose chart below:

T-CUPS:

Tolvaptan use in Cystinuria and Urolithiasis: A Pilot Study

DOSING SCHEDULE by WEIGHT

Weight (kg)	Day 1-4	Day 5-8
12.5 kg -37.49 kg (mean=25kg) For illustration: We will not recruit anyone weighing less than 25kg.	7.5mg (.6mg/kg - .2mg/kg)	15mg (1.2mg/kg - .4mg/kg)
37.5kg-62.49kg (mean =50kg)	15.0 mg (.4mg/kg - .24 mg/kg)	30mg (.8mg/kg - .48mg/kg)
62.5 kg -87.49kg (mean 75kg)	22.5 mg (.36mg/kg - .26mg/kg)	45.0mg (.72mg/kg - .52mg/kg)
87.5 kg – 112.49kg (mean 100kg)	30.0 mg (.34mg/kg - .27mg/kg)	60.0mg (.68mg/kg - .54mg/kg)
112.5kg – 137.5kg (mean 125kg)	37.5 mg (.33 mg/kg - .27mg/kg)	60.0mg (.66mg/kg - .54mg/kg)

This daily dose will continue for a total of 4 doses, through Day 4. On Day 5, the dose will be increased per chart, up to a maximum dose of 60 mg. If tolerated, the higher dose will be continued for a total of 4 doses through Day 8. No drug will be given on day 9 or 10.

Tolvaptan is produced commercially as 15 mg triangular tablets and 30 mg round tablets.

Patients currently on chelation therapy will NOT discontinue these medications during the study period.

(4) Definition of Primary and Secondary Outcomes/Endpoints

The primary outcome will be urinary cystine levels as measured by cystine capacity (Litholink Corp; mg/L). Four 24-hour urine samples will be obtained during the study: one at baseline 3-6 days prior to the measurement, one on day 3-4 of the dosing period, one on day 7-8 of the dosing period, and one 3-6 days after the washout period. Each 24 hour urine sample will be sent individually for analysis by Litholink Corp, which performs the cystine assays.

Secondary outcomes will include daily urine output and urine osmolality. Additional data points to be collected include serum sodium and other electrolyte levels, serum osmolality, plasma AVP concentration, and urinary electrolytes and osmolality. Urinary symptoms will be measured with the AUA symptom score.

(5) Data Collection Methods, Assessments, Interventions and Schedule (what assessments performed, how often)

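### The electrolyte and cardiovascular safety summary has no dose split, time window or baseline reference, so it cannot show when abnormal values arose

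*Combined protocol and SAP*

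**What the plan says.** The rule is in Section I (Statistical Power and Sample Considerations). Electrolyte and cardiovascular measures are to be analysed by the "proportion of subjects experiencing at least one outlier measurement", where an outlier is "defined as a clinically abnormal value based on the standard normal range for each test". The proportion is formed separately, "for each parameter (each of the serum chemistry values, and cardiovascular measures".

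The measurements come from distinct periods:

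- Section D(6): "The day prior to the treatment period (Day 0) will be used to obtain baseline clinical and laboratory data".
- Section D(6): "Study drug will be administered starting on Day 1 through Day 8, with a 2 day washout period on days 9 and 10".
- Section D(3): "On Day 5, the dose will be increased per chart, up to a maximum dose of 60 mg".
- Section E: "Serum Electrolytes will be checked on days 0, 2, 4, 6, 8,and 10".

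Section E also has round-the-clock vital signs in the two inpatient 24-hour periods that follow the Day 1 and Day 5 doses, and checks vital signs at outpatient visits on the other treatment days. It allows a subject with an adverse reaction on the higher dose to return to the lower one.

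Section H does separate baseline, low-dose and high-dose phases, but only for cystine capacity. Section I classifies adverse effects by their consequence, not by dose.

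**The concern.** Aim 1 is the short-term safety profile, and Hypothesis 1a predicts little electrolyte disruption and no detectable cardiovascular change. Both are statements about what happens on drug relative to off drug. The trial has one arm, so each subject's own periods are the only comparators available. A yes/no score over an unstated window, set against a population range, discards that comparison.

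What is at stake is whether the main quantitative summary for Aim 1 can be interpreted. A reported proportion of, say, 2 of 8 would read the same whether both subjects were abnormal only on the lower dose or only on the higher dose.

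**Working it through.** **Step 1: what the rule does, without assumptions.** Consider four hypothetical subjects with abnormal sodium on these days only:

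| Abnormal on | Period | Score if all draws count | Score if only on-drug draws count |
|---|---|---|---|
| Day 0 | pre-dose | yes | no |
| Days 2, 4 | lower dose | yes | yes |
| Days 6, 8 | higher dose | yes | yes |
| Day 10 | off drug | yes | no |

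On either reading the second and third subjects cannot be told apart. With no baseline reference, a subject abnormal on Day 0 and unchanged throughout also scores yes on either reading.

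**Step 2: inputs for an illustration.** From the documents: six electrolyte draws, of which four are on drug, two per dose period (Section E with Sections D(3) and D(6)); 16 recruited to obtain 8 completers (Section D(2)). The documents give no background outlier rate and no planned safety figure, so there is nothing to reproduce. Assumed: no drug effect, and a chance q that a single draw is outside the range, with q = 0.05 as the main case and 0.01 to 0.10 as the range.

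**Step 3: independent draws.** P(at least one outlier in k draws) = 1 − (1 − q)^k. At q = 0.05:

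- six draws: 1 − 0.95^6 = 1 − 0.7351 = 26.5%; × 8 = 2.1 subjects
- four on-drug draws: 1 − 0.95^4 = 1 − 0.8145 = 18.5%; × 8 = 1.5
- two draws in one dose period: 1 − 0.95^2 = 1 − 0.9025 = 9.75%; × 8 = 0.8
- Day 0 or Day 10 alone: 5%; × 8 = 0.4

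The multiplication by 8 uses completers. The plan does not say which set of subjects the safety summary uses.

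If all six draws count, the share of flagged subjects who are flagged only on Day 0 and/or Day 10 is 0.95^4 × (1 − 0.95^2) / 0.2649 = 0.8145 × 0.0975 / 0.2649 = 30%.

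**Step 4: range of q, independent draws.**

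| q | Six draws | Four on-drug draws | One dose period |
|---|---|---|---|
| 0.01 | 5.9% | 3.9% | 2.0% |
| 0.05 | 26.5% | 18.5% | 9.75% |
| 0.10 | 46.9% | 34.4% | 19.0% |

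**Step 5: correlated draws.** Simulation of 400,000 subjects with normally distributed values, two-sided 5% limits (q = 0.05) and a common within-subject correlation (ICC):

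| ICC | Six draws | Four on-drug draws | One dose period |
|---|---|---|---|
| 0.3 | 24.1% | 17.4% | 9.5% |
| 0.5 | 20.7% | 15.5% | 9.0% |
| 0.7 | 16.4% | 13.0% | 8.4% |
| 0.9 | 10.8% | 9.3% | 7.0% |

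The size of the gap depends on q and the correlation. Its direction does not: the pooled figure exceeds the per-period figure throughout.

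**The case against.** The best case for the plan is that this is a descriptive pilot. No threshold or go/no-go rule depends on the proportion. Values are collected by study day, so individual profiles of 8 to 16 subjects could be inspected whatever Section I says. That stands, and it limits the severity. It does not rescue the summary, because the stated analysis would not report the values that way.

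Several stronger readings are tempting and are not supported:

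- **That the plan expressly counts Day 0 and Day 10 values.** It does not. The window is unstated, and Section D(6) treats Day 0 as baseline. The point rests on merging the two doses, which happens on either reading.
- **That about a quarter of subjects will be flagged by chance.** The 26.5% needs all six draws to count, independence and an assumed 5% rate. Repeat draws within days of each other are probably correlated, and a clinically abnormal value need not be a 5% statistical tail.
- **That unequal numbers of readings bias the result.** Section I compares no groups or periods, and all subjects share one schedule unless they stop early. Section E does not say how many vital-sign readings are taken at an outpatient visit. Differing intensity matters once periods are compared, so the revised table has to allow for it.
- **That a by-period table would attribute abnormalities to the drug or dose.** The order is always low then high, with no concurrent control, so dose remains confounded with time.

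**Conclusion.** The point holds in a limited form. As written, Section I merges the lower and higher dose on any reading, and pre-dose and off-drug values too if all draws count. With no baseline reference, it cannot separate pre-existing abnormalities from those arising on treatment or on escalation.

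That conclusion follows from the text and needs no numerical assumption. The percentages only illustrate it. With no drug effect and an assumed 5% rate per draw, six-draw pooling flags 26.5% of subjects under independence and 24% to 11% at correlations of 0.3 to 0.9. The corresponding figures for one dose period are 9.75% and 9.5% to 7.0%.

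The sample size and the primary efficacy analysis are unaffected. This is a worthwhile, inexpensive improvement to the Aim 1 analysis and not a flaw in the data collection.

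**What to change.** In Section I:

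1. Tabulate the outlier proportion for each parameter by period: Day 0; lower dose; higher dose; Day 10. Assign treatment-period values by the dose actually taken, since a return to the lower dose is possible. Show Day 10 separately, because it falls two days after the last scheduled dose and carry-over is possible. State the number of subjects with data in each cell.
2. Add a shift-from-Day-0 display for each parameter. It should retain subjects already abnormal at baseline and show any worsening. Counting only subjects normal on Day 0 would hide such worsening.
3. For vital signs, show the two inpatient 24-hour periods (from Day 1 and from Day 5) separately from outpatient visits, because monitoring intensity differs. Both inpatient periods are on drug, so that pair contrasts the doses and does not give a drug-versus-no-drug comparison.
4. State that dose is confounded with time in this single-arm, fixed-order design, so attribution is only partly restored.
5. State whether the outlier rule covers liver tests, which follow their own schedule (Section E: "Liver function tests will be obtained at baseline, Day 4, and Day 8, and Day 10").

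The cost is re-tabulation and smaller counts per cell. No additional tests, visits or subjects are needed.

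### The proportion of subjects with any abnormal value mixes drug effect with number of readings, because on-drug periods are read far more often than off-drug visits

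*Combined protocol and SAP*

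**What the plan says.** Section I gives the only planned summary of electrolyte and cardiovascular safety: the "proportion of subjects experiencing at least one outlier measurement (defined as a clinically abnormal value based on the standard normal range for each test"). The rule is applied separately to every chemistry value and every cardiovascular measure. It does not say which readings count, does not split by phase, and refers to no baseline value. On its plain reading, every measurement counts.

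Section E sets how often vital signs are read. Subjects are inpatients "for 24 hours after the initial dose (Day 1) and also for 24 hours after the increased dose (Day 5"). In both of those inpatient stays, "subjects will undergo around the clock monitoring of vital signs and daily input and outputs". On other days, "At each outpatient visit vital signs will be checked". The interval between inpatient readings is not given.

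Section D(3) adds: "Starting at between 10AM and 2PM on Day 1, Tolvaptan will be administered orally". In Section D(6), "The day prior to the treatment period (Day 0) will be used to obtain baseline clinical and laboratory data". The schedule in Section D(5) makes Day 0 and washout Days 9 and 10 outpatient visits. Section E puts serum electrolytes on Days 0, 2, 4, 6, 8 and 10, and liver tests at baseline and Days 4, 8 and 10.

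Section D(1) describes a single unblinded arm. Hypothesis 1a in Section A expects little electrolyte disturbance and no detectable change in blood pressure or other cardiovascular measures.

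**The concern.** The chance that a subject has at least one value outside a normal range grows with the number of values taken, whether or not the drug does anything. Here the number of values is tied to treatment. Both periods of intensive vital-sign monitoring follow a dose, and no off-drug night reading is scheduled. No control arm is monitored in the same way.

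Hypothesis 1a is a statement about change, so a reader will want an off-drug reference. The only one available is a few outpatient readings. A high proportion could then reflect the drug, the reading count or ordinary night values, and the planned summary cannot tell these apart. With eight completers, two chance flags already read as 25%.

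**Working it through.** The plan states no expected outlier rate or other figure for this outcome, so there is nothing to reproduce. The check asks how many subjects would be flagged with no drug effect.

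**Inputs from the documents**
- Off-drug vital-sign visits: Days 0, 9 and 10 (Sections D(5) and D(6)).
- On-drug visits: Days 2–4 and 6–8, six in all (Section E).
- Two on-drug 24-hour inpatient periods (Section E).
- Electrolyte draws: one baseline, four on drug (Days 2, 4, 6, 8), one washout (Day 10).
- Eight complete participants (Section D(2)).

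**Assumptions, not in the documents**
- One vital-sign reading per visit, and inpatient readings every 4 hours (range: 8-hourly to hourly).
- Chance p that one reading falls outside the range: 5% or 1%.
- Equal correlation ρ between a subject's readings: 0, 0.5 or 0.8, with normally distributed values.

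**Step 1: reading counts.** Off drug: 3. On drug, 4-hourly: 6 + 2 × 6 = 18. For 8-, 2- and 1-hourly readings: 6 + 2 × 3 = 12, 6 + 2 × 12 = 30 and 6 + 2 × 24 = 54.

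**Step 2: independent readings.** P(at least one flag in k readings) = 1 − (1 − p)^k.
- p = 5%: 1 − 0.95^18 = 0.603, against 1 − 0.95^3 = 0.143.
- p = 1%: 1 − 0.99^18 = 0.165, against 1 − 0.99^3 = 0.030.

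**Step 3: correlated readings.** P = 1 − ∫ [Φ((c − √ρ z)/√(1 − ρ)) − Φ((−c − √ρ z)/√(1 − ρ))]^k φ(z) dz, where c is the two-sided normal limit for p, evaluated numerically.

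| Vital signs, no drug effect | ρ = 0 | ρ = 0.5 | ρ = 0.8 |
|---|---|---|---|
| p = 5%, 18 on-drug readings | 60% | 40% | 22% |
| p = 5%, 3 off-drug readings | 14% | 13% | 10% |
| p = 1%, 18 on-drug readings | 17% | 11% | 6% |
| p = 1%, 3 off-drug readings | 3% | 3% | 2% |

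Of eight subjects, per vital sign, the 5% rows give 4.8, 3.2 and 1.7 on drug against 1.1, 1.0 and 0.8 off drug. The 1% rows give 1.3, 0.9 and 0.5 against about 0.2.

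**Step 4: reading interval.** With independent readings at 8-, 4-, 2- and 1-hourly intervals, the on-drug figure is 46%, 60%, 79% and 94% at p = 5%, and 11%, 17%, 26% and 42% at p = 1%.

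**Step 5: night values.** Suppose one third of inpatient readings (4 of 12) fall at night with a mean 1 SD lower, again an assumption. At p = 5%, one night reading's flag chance rises from 5% to 17%. The 18-reading figure rises from 40% to 58% at ρ = 0.5, and from 22% to 40% at ρ = 0.8.

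**Step 6: chemistry.** Four on-drug draws against one baseline draw give 19%, 16% and 11% against 5% at p = 5%, and 4%, 3% and 3% against 1% at p = 1%. Liver tests have only two on-drug draws: 10%, 9% and 8% against 5% at p = 5%.

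**Step 7: equal counts.** Three visit readings in each of Days 0/9/10, Days 2–4 and Days 6–8 give the same no-effect figure in every phase: 14%, 13% and 10% at p = 5%. The imbalance disappears by construction.

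**The case against.** The strongest reply is that this is a descriptive safety screen. Section I rules out statistical analysis of adverse effects, sets no threshold and plans no comparison of on-drug with off-drug readings. No type I error is at stake. In a pilot with eight completers, counting any abnormal value is a cautious choice, and taking the readings after the first and the increased dose out of view would be a loss. The low- and high-dose phases each contain one inpatient period, so a comparison between them is roughly balanced. The size of the effect also rests on an unstated interval, rate and correlation.

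All of this stands, and it limits the point. It is a reason to keep the any-reading proportion, not to rely on it alone: the absolute level and any contrast with off-drug readings still depend on reading count.

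Two stronger readings are tempting and are not supported.
- A reader might infer that chance flags would contradict Hypothesis 1a. The hypothesis has no numerical criterion, and the size is assumption-driven. The documents support only that the proportion cannot be interpreted against it.
- A reader might infer that subjects who tolerated the drug longest would look least safe, because early stoppers have fewer readings. But the sodium, potassium and CO₂ stopping criteria in Section E are themselves values outside the normal range, so subjects stopped for them are already counted. Tachycardia or hypotension would usually count too. Only stops for symptoms could escape, and Section I separately classifies adverse effects by whether they led to discontinuation.

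**Conclusion.** The point holds in a limited form. The only planned summary of electrolyte and cardiovascular safety combines drug effect with monitoring intensity, and it offers no phase split or Day 0 reference to separate them. For vital signs with 4-hourly readings and no drug effect, the on-drug proportion is about 2 to 5 times the three-visit off-drug proportion: 22% against 10% up to 60% against 14% at a 5% rate, and 6% against 2% up to 17% against 3% at 1%. For electrolytes, four draws against one give 11% to 19% against 5% at the 5% rate.

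The direction holds under every assumption tried; the size does not come from the documents. That subjects are asleep for some inpatient readings is an inference: a 24-hour period must include a night, but the plan does not mention sleep. The night issue concerns vital signs only. This is worth correcting because the repair is cheap, but it does not undermine the trial's safety monitoring.

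**What to change.** In Section I, keep the any-reading proportion and all inpatient readings as a safety display, and show the number of readings per subject beside each proportion. Add one table:

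- **Cardiovascular measures:** the proportion of subjects with an abnormal value by phase, from the existing visit readings with equal counts: Days 0/9/10, Days 2–4 and Days 6–8. State which reading counts on Days 2 and 6, when subjects are discharged.
- **Chemistry:** baseline, low dose, high dose and washout shown separately, each with its number of draws.
- **Both:** mark abnormalities that are new since Day 0.

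State that conclusions on Hypothesis 1a rest on this table rather than on the any-reading proportion.

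The cost is Section I wording and one extra table. No new measurement and no common clock time are needed. Pooling a single daytime reading per day over Days 0 to 10 would not be enough: those 11 readings still flag 43%, 30% or 18% of subjects by chance at the 5% rate (ρ = 0, 0.5, 0.8), and drug and off-drug days stay mixed.
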